14.0 DATA HANDLING AND RECORD KEEPING

14.1 Confidentiality

Information about study participants will be kept confidential and managed according to the requirements of the Personal Health Information Protection Act of 2004 (PHIPA) and the Research Ethics Board. PHIPA outlines the rules for the collection, use and disclosure of personal health information. The Act requires each participant to consent to the collection, use and access of personal health information (PHI), unless consent is waived by the REB. As consent is required, each participant will be informed of the following:

- What PHI will be collected during this study
- Who will have access to that information and why
- Who will use or disclose that information
- The rights of a research participant to revoke their authorization for use of their PHI.

In the event that a participant revokes authorization to collect or use PHI, the investigator may use all information collected prior to the revocation of participant authorization. For participants that have revoked authorization to collect or use PHI, attempts should be made to obtain permission to collect at least vital status (i.e. that the participant is alive) at the end of their scheduled study period.

14.2 Source Documents

Source data/documents are original documents, data and records in a clinical study that are necessary for the reconstruction and evaluation of the study. Original documents and data records in this study include, but are not limited to:

- Worksheets
- hospital records
- medical records
- memorandum
- participants' diaries or evaluation checklists
- pharmacy dispensing records
- copies or transcriptions certified after verification as being accurate and complete
- participant files and records kept at the pharmacy
- entries entered directly into the source documents

Source documents have been developed for the baseline assessment (including, medical history), week 1 contact information, week 4 contact information, , week 8 contact information, week 12 contact information, week 12 assessment, week 12 pill count, side effect questionnaire and quality of life questionnaire, and protocol deviations.

Each participating site will maintain appropriate medical and research records for this study, in addition to regulatory and institutional requirements for the protection of confidentiality of participants. If electronic source data documents are printed it should be signed and dated by the investigator to confirm content and filed with other source documents.

The investigator(s) and research team members listed on the Task Delegation Log (TDL) will have access to participant medical records and will collect only the information needed for the study.

Sponsor delegated monitors, representatives of institutional committees and regulatory authority representatives of the country in which the study is being conducted will also have access to examine records for the purposes of quality assurance reviews, audits and evaluation of study safety and progress.

14.3 Data Management Responsibilities

Data collection and accurate documentation are the responsibility of the study personnel under the supervision of the investigator. All source documents and applicable laboratory reports will be reviewed as needed and used to ensure that data collected for the purposes of the study are accurate and complete. Contemporaneous review of laboratory results and the assessment of clinical significance for those results considered out of range will be documented by means of dated signature by the reviewing investigator. Study personnel, including data entry team members, should use source documents to complete case report forms (CRFs).

As part of the safety plan for this study, the investigator will review individual study participant records to ensure that appropriate mechanisms to protect the safety of study participants are being followed, that protocol requirements are being adhered to, and that data is accurate, complete, and secure. Participant records include, but are not limited to: consent forms, case report forms, data forms, laboratory specimen records, inclusion/exclusion forms, and medical charts. All study data will be collected by a member of the study research team and recorded in accordance with applicable procedures.

14.4 Data Capture

14.4.1 Case Report Forms

The study case report form (CRF) is the primary data collection instrument for this study. Electronic/Paper case report forms (eCRFs/pCRFs) will be used to collect data for this study. CRFs will be completed by data capture personnel and signed off by the investigator in a timely manner. Good documentation practices will be implemented according to standard operating procedures. All data requested on the CRF must be recorded and verifiable by source document.

14.5 Records Retention

It is the responsibility of the REB, investigator and regulatory sponsor to retain study essential documents as per local regulatory requirements and GCP Guidelines.

Study essential documents must be maintained in a secure and confidential manner for participating Canadian sites for a period of 25 years. For the purposes of this study, the start date of the retention period is the date of the final report of the trial. Exceptions may be made for sites which close prematurely, wherein the start date for the retention period will be the date of notification to Health Canada of the sites closure. All study records are then to be destroyed according to local and national policy and requirements. It is the investigator's responsibility to request authorization for destruction at the completion of the retention period and/or for the sponsor to inform the investigator/institution when these documents may be destroyed.

APPENDIX A:

WHO Bleeding Severity Scale⁴³

	Grade 1	Grade 2	Grade 3
Oral and nasal	
 ➤ Oropharyngeal bleeding – total duration of all episodes in previous 24 hours ≤30 minutes* ➤ Petechiae of oral mucosa ➤ Epistaxis – total duration of all episodes in previous 24 hours ≤30 minutes* 	
 ➤ Oropharyngeal bleeding – total duration of all episodes in previous 24 hours >30 minutes* ➤ Epistaxis – total duration of all episodes in previous 24 hours >30 minutes* 	
 ➤ Any bleeding requiring RBC transfusion over routine transfusion needs†
Skin, soft tissue, musculoskeletal	
 ➤ Petechiae of skin ➤ Purpura ≤1 inch diameter ➤ One or more spontaneous hematomas in the soft tissue or muscle >1 inch 	
 ➤ Purpura >1 inch diameter ➤ Spontaneous hematoma in deeper tissues ➤ Joint bleeding (confirmed by aspiration, imaging study or other accepted technique) 	
 ➤ Any bleeding requiring RBC transfusion over routine transfusion needs†
Gastrointestinal	
 ➤ Positive stool occult blood test‡ 	
 ➤ Melanotic stool ➤ Hematochezia – visible red blood mixed in stool, not requiring a transfusion ➤ Hematemesis – grossly visible blood in emesis or in nasogastric drainage tube (not related or secondary to swallowed blood) 	
 ➤ Any bleeding requiring RBC transfusion over routine transfusion needs†
Genitourinary	
 ➤ Any biochemical or microscopic Hb/RBCs without red urine‡ ➤ Abnormal vaginal bleeding (unexpected bleeding out of normal cycle or bleeding heavier than normal or breakthrough bleeding (patient on hormonal therapy to 	
 ➤ Gross/visible hematuria without need for transfusion ➤ Abnormal vaginal bleeding (unexpected bleeding out of normal cycle or bleeding heavier than normal or breakthrough bleeding (patient on hormonal therapy to 	
 ➤ Any bleeding requiring RBC transfusion over routine transfusion needs†

	prevent bleeding)) with spotting	prevent bleeding)) more than spotting	
Pulmonary		
 ➤ Hemoptysis – visible blood ➤ Blood in broncho-pulmonary lavage, or blood tinged sputum (excluding those with nose or oropharyngeal bleeding) 	
 ➤ Any bleeding requiring RBC transfusion over routine transfusion needs†
Body cavity		
 ➤ Visible blood in body cavity fluid (e.g. red cells apparent in fluid aspirate) shore of criteria for Grade 3 or 4 	
 ➤ Grossly bloody body cavity fluids and organ dysfunction with symptoms, and/or need to intervene (e.g. to aspirate), and/or need for transfusion
Central nervous system		
 ➤ Retinal bleeding without visual impairment ➤ Lumbar puncture with blood (>5 RBC/µL in CSF on microscopic analysis and non-traumatic tap), no symptoms and no visible red color 	
 ➤ Lumbar puncture with visible red color in absence of symptoms, and non-traumatic tap
Invasive sites		
 ➤ Bleeding at invasive sites (venipuncture sites, intravenous lines or catheter exit sites): active oozing at site for a cumulative total of >1 hour in the previous 24 hours 	
 ➤ Any bleeding requiring RBC transfusion over routine transfusion needs†
Hemodynamic instability			
 ➤ Any bleeding associated with moderate hemodynamic instability (hypotension; >30mmHg fall or >30% decrease in either systolic or diastolic blood pressure) and requiring RBC transfusion over routine transfusion needs†
Grade 4:			

- Any bleeding associated with severe hemodynamic instability (hypotension; >50mm/Hg fall or >50% decrease in either systolic or diastolic blood pressure, with associated tachycardia (heart rate increase of ≥20% for 20 minutes) and requiring RBC transfusion over routine transfusion needs
- Fatal bleeding from any source
- Retinal bleeding with visual impairment (Visual impairment is defined as a field deficit, and patients with suspected visual impairment require an ophthalmologic consult for documentation)
- CNS symptoms with non-traumatic bloody lumbar puncture
- CNS bleeding on imaging study with or without dysfunction

RBC indicates red blood cell; Hb, hemoglobin; CSF, cerebrospinal fluid; Hg, mercury; and CNS, central nervous system

*Count actual bleeding (i.e. “running out” or need for basin, Kleenex, towel, etc.) not minor bleeding

†Red cell transfusion must be specifically related to treatment of bleeding within 24 hours of onset of bleeding

‡Not assessed in PLADO

APPENDIX B:

Pictorial Blood Assessment Chart (PBAC) for menstrual bleeding^{44,45}

A score of > 100 on the PBAC is defined as menorrhagia.

Pictorial Blood Loss Assessment Chart

DAY	DAY1	DAY2	DAY3	DAY4	DAY5	DAY6	DAY7	DAY8	DAY9	DAY10	TOTAL TALLIES	MULTIPLYING FACTOR	ROW TOTAL
												X1	
												X5	
												X20	
												X1	
												X5	
												X10	
Small blood clots (= Dime)												X1	
Large blood clots (≥ Quarter)												X5	
Menstrual accidents												X5	
Total Score (Sum of rows)													

How to use the Pictorial Blood Assessment Chart:

- Record the number of tampons and sanitary pads used each day during your period by placing a tally mark under the day next to the box representing the amount of bleeding noted each time you change your pads or tampon (see example at right)
- Record clots by indicating whether they are the size of a dime or a quarter coin in the small and in the large blood clot row under the relevant day.
- Record any incidences of flooding (accidents) by placing a tally mark in the menstrual accident row.

Scoring the Chart:

At the end of your period tabulate a "Total Score" by multiplying the total number of tallies in each row by the "Multiplying Factor" at the end of the row. Then sum the "Row Totals" to obtain the final "Total Score".

Example:

[name] in the first day of her period, she used 7 pads (5 lightly stained, 1 moderately and 1 heavy stained). She also used 1 moderately stained tampon and had 3 blood clots 1 small and 2 large. She also had one incidence of flooding.

Days	D1	D2	D3	D4
Small blood clots (= Dime)				
Large blood clots (≥ Quarter)				
Menstrual accidents				
Total Score				

Completed by: _____

Date: _____

Reviewed by: _____

Date: _____

APPENDIX C:

Table 1: Flow Chart of Assessments/Procedures to be Performed Throughout the Study

Procedures	Prior to Enrolment	After Enrolment	Week 1 (±3 days)	Week 4 (±7 days)	Week 8 (±7 days)	Week 12 (±7 days)	Week 13 (7 days ± 3 days after final study visit)
Referring clinician offices identify potential patients as participants	X						
Patient (surrogate) informed consent	X						
Inclusion and exclusion criteria	X						
Randomization		X					
Baseline Data							
Case Logs (reason for lack of consent, protocol violations)	X						
Medical History		X					
Laboratory Assessments							
Hemoglobin	X			X		X	
Reticulocyte Count	X			X		X	
C reactive protein (CRP) – acute phase reactant	X						
Ferritin	X					X	
Serum Iron	X					X	
Transferrin Saturation (TSAT)	X					X	
Creatinine clearance	X						
Subjective Patient Assessments							
FACIT-Fatigue Scale Questionnaire		X		X	X	X	
Patient Diary Adherence			X reminder	X	X	X	
Side Effect Questionnaire				X	X	X	
Pill Count						X	
Adverse and Serious Adverse Events			X	X	X	X	X
Need for Therapy Escalation			X	X	X	X	

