Another potential recruitment site will be through Canadian Blood Services. Blood donors that have been deferred due to low hemoglobin levels (within the local Toronto area close to hospital study sites) will be provided with a letter (see Supporting Documents) which explains that the donor was deferred and for the donor to see visit their family physician for further investigation. In addition, a letter to the family physician will explain key points about the study purpose, rationale, procedures and detailed information about the DEODO trial. If the patient is interested in participating in the study, after visiting their family physician, the family physician can refer the patient to one of the study sites. The letter contains contact information for the Principal Investigator and Research Coordinator if the patient or their family physician has any questions. It is also acceptable for the patient to contact the study site directly in which case permission from the MRP is not required. Once the patient is referred to or has contacted a study site, then consent will occur as outlined in the previous paragraph.

Once the patient has consented, bloodwork will be performed at the participating institution's laboratory or at a local lab, if it has not been performed in the past 2 weeks. Eligibility of the patient will be determined. If the eligibility is confirmed, then the patient will be enrolled (assigned a study ID) and randomized. Any additional bloodwork required within the pre-specified time frame (see 5.4.1.2) can be drawn or added on to the bloodwork already completed.

All sites will obtain Research Ethics Board (REB) approval of the protocol and the informed consent form. A recruitment log of eligible and ineligible patients as well as reasons for non-consent will be kept at each participating centre. We anticipate that this study will take 2 years to complete.

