5.3.2 Randomization and stratification

Randomization allocation will be performed by Clinical Trial Services at Sunnybrook Health Sciences Centre using a computer generated allocation sequence. The randomization code will be generated in random blocks of 4 to 6, stratified by centre, and hemoglobin at time of randomization (hemoglobin greater or equal to 100 g/L or less than 100 g/L). Randomization will be provided to the sites in opaque numbered envelopes. The study is an open-label study. The research coordinator/assistant will enroll participants for this study.

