5.4 Study Visits and Assessments

5.4.1 Baseline Visit and Assessment

Baseline assessment will occur according to the schedule below and may be performed in person/remotely (telephone/zoom/OTN). The following assessments will be completed at baseline:

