5.4.1.1 Screening and enrollment will occur within 1 week of randomization

Case logs will be initiated for each referral meeting inclusion criteria, indicating:

- Any applicable exclusion criteria as listed in 5.2.2
- Reason for lack of consent amongst eligible patients
- Protocol violations for enrolled patients

Medical history:

- Demographics: age, sex, height, weight
- Diagnosis (reason for iron deficiency anemia, if known)
 - Example: gynecological, gastrointestinal, urologic, blood donation

- History of observed bleeding in the past 2 months: Y/N
 - Location of bleeding
 - Severity by WHO grade 1-3 (see Appendix A)
 - If menstrual bleeding, use validated tool (see Appendix B)
- Diet
 - Vegetarian
 - Vegan
- Blood Donation: Y/N
 - Number of times in past year?
 - Number of times in past 4 months?
- Comorbidities
 - Rheumatologic disorders: e.g. SLE, rheumatoid arthritis
 - Smoking
- Medication history at time of enrollment
 - Ranitidine
 - Proton pump inhibitor use
 - Medications
 - Other vitamin supplements (not including iron)
- History of oral iron use: Y/N
 - Any iron use in the past year: Y/N
 - If yes, last oral iron intake: (date)
 - Type of oral iron and tolerability
- History of IV iron use in the past year: Y/N
 - Type of IV iron

Questionnaire:

- FACIT-Fatigue scale (see Supporting Documents)

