7.2 Secondary outcome assessments

Feasibility

1. Proportion of eligible patients consenting to participate

$$\frac{\# \text{ meeting eligibility criteria} - \# \text{ in whom consent not obtained}}{\# \text{ meeting eligibility criteria}}$$

2. Proportion of consenting patients receiving the allocated treatment

consenting to treatment - # not administered allocated treatment
consenting to treatment

3. Proportion of treated patients completing 4 week and 12 week laboratory tests

completing 100% of 4 week and 12 week lab tests
consenting to treatment

4. Proportion of treated patients completing 4 week, 8 week and 12 week side effect questionnaire

completing 100% of 4 week, 8 week and 12 week side effect questionnaire
consenting to treatment

5. Proportion of treated patients completing 4 week, 8 week and 12 week FACIT-fatigue scale

completing 100% of 4 week, 8 week and 12 FACIT-fatigue scale
consenting to treatment

6. Proportion of treatment doses taken as per protocol based on pill count

$$\frac{\text{total # of doses} - \text{# of missed doses}}{\text{total # of doses}}$$

7. Proportion of treated patients taking at least 90% of their prescribed doses

$$\frac{\text{# of patients taking at least 90% of prescribed doses}}{\text{total # of treated patients}}$$

8. Proportion of treated patients requiring a step down in therapy

$$\frac{\text{# of patients requiring step down in therapy}}{\text{total # of treated patients}}$$

Clinical/Safety

9. Hemoglobin increment at 4 and 12 weeks is defined as the 4 or 12 week hemoglobin value minus the baseline hemoglobin value

10. Proportion with complete hemoglobin response defined as hemoglobin greater than or equal to 120 g/L in women; and 130 g/L in men at 4 weeks and 12 weeks

11. Change in reticulocyte count at 4 and 12 weeks defined as the 4 or 12 week reticulocyte count minus the baseline reticulocyte count

12. Change in ferritin, serum iron and TSAT at 12 weeks defined as the value at 12 weeks minus the baseline value

13. Quality of life (FACIT-fatigue scale) at 4, 8 and 12 weeks

14. Proportion with side effects and type of side effects at 4, 8 and 12 weeks as determined by the oral iron side effect questionnaire
15. Proportion of patients who stop taking oral iron due to side effects at 4 and 12 weeks

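### The schedule does not ensure that baseline FACIT-fatigue precedes disclosure of the arm, and the FACIT outcome leaves that baseline unused: a precision loss that can be repaired at almost no cost

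*Combined protocol and SAP*

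**What the plan says.** **Timing.** Appendix C has one column for steps before enrolment and one for steps after it. Consent, the eligibility check and all baseline laboratory tests are marked in the first. "Randomization", "Medical History" and the first "FACIT-Fatigue Scale Questionnaire" are marked only in the second, apart from the later FACIT assessments.

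Section 5.3.1 says that once eligibility is confirmed, "then the patient will be enrolled (assigned a study ID) and randomized"; no questionnaire is placed between the two steps. Section 5.4.1 introduces medical history and FACIT with "The following assessments will be completed at baseline". The only timing attached to them is the heading of 5.4.1.1, "Screening and enrollment will occur within 1 week of randomization". Section 5.3.2 has allocation supplied in envelopes and adds: "The study is an open-label study".

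**Outcome.** Section 7.2 defines the hemoglobin, reticulocyte, ferritin, serum iron and TSAT outcomes as follow-up minus baseline. Item 13 reads only "Quality of life (FACIT-fatigue scale) at 4, 8 and 12 weeks"; the protocol summary and section 3.4 use the same time points. Section 8.2 summarizes continuous data by means and SDs or medians and quartiles. It names neither a change score nor a baseline-adjusted comparison for FACIT.

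**The concern.** FACIT-fatigue is self-reported. A score given after the patient has been told daily or every other day is not a clean pre-treatment value, because the answer may reflect a reaction to the assigned frequency. If such a score were used as the baseline, any arm-specific reaction would carry into the treatment comparison, and a larger sample would not remove it.

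The outcome definition raises a separate question. The trial collects a baseline fatigue score from every patient, but the stated outcome does not use it. In a pilot expecting 36 evaluable patients, that discards information which could narrow a wide interval. The results are meant to inform the definitive trial, so both the schedule and the outcome definition may be carried forward.

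**Working it through.** **1. The plan's own figure.** The documents give no FACIT sample-size or precision figure. The number per arm comes from section 8.1, Table 2 (true difference 0, SD 5, margin 5, power 90%, one-sided 5%):

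n per arm = 2 × SD² × (z₀.₉₅ + z₀.₉₀)² / margin² = 2 × 25 × (1.645 + 1.282)² / 25 = 17.1, rounded up to 18, or 36 in total. The noncentral-t calculation also gives 36. With 30% dropout, 36 / 0.70 = 51.4, rounded up to 52. Both figures match the plan. They are used here only to set 18 evaluable per arm (section 4.0 also gives 36).

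**2. What the schedule allows.** FACIT and randomization share a column, and enrolment runs straight into randomization. Under 5.3.3.2 the prescription follows randomization, and under 5.3.3.5 and 5.3.3.6 dosing starts on Day 1. Nothing ties FACIT to a point before the envelope is opened or before the first tablet. A site can follow every written instruction with FACIT taken on either side of disclosure. The FACIT completion measures count only weeks 4, 8 and 12, so they would not reveal a late or missing baseline.

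**3. When a disturbed baseline matters.** Suppose knowing the arm shifts the between-arm difference in baseline FACIT by d points and leaves follow-up unchanged. Let ρ be the baseline to follow-up correlation, with equal SDs. The bias in the follow-up comparison is then:

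- follow-up scores only (the outcome as written): 0
- change from baseline: −d
- adjusted for baseline (ANCOVA): −ρd

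The documents give no basis for a value of d.

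**4. Precision.** The SDs are 10.82 and 11.64, the two hemoglobin groups in section 2.1.7. With n = 18 per arm, the half-width on raw scores is 1.96 × SD × √(2/n):

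- 1.96 × 10.82 × √(2/18) = 7.07
- 1.96 × 11.64 × √(2/18) = 7.60

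Multiply by √(1 − ρ²) for baseline adjustment and by √(2(1 − ρ)) for a change score. The values of ρ are assumptions.

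| ρ (assumed) | Raw follow-up | Adjusted for baseline | Simple change |
|---|---|---|---|
| 0.3 | 7.1-7.6 | 6.7-7.3 | 8.4-9.0 |
| 0.5 | 7.1-7.6 | 6.1-6.6 | 7.1-7.6 |
| 0.7 | 7.1-7.6 | 5.0-5.4 | 5.5-5.9 |

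If all 26 per arm were evaluable, the raw half-width would be 5.9-6.3. The adjusted values would be 5.6-6.0, 5.1-5.5 and 4.2-4.5 in the same order of ρ.

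Adjustment is at least as precise as raw scores at every ρ. A change score beats raw scores only when ρ exceeds 0.5.

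**The case against.** The strongest reply is that the text leans toward a pre-randomization baseline. The column is headed by enrolment, not by randomization. Section 5.3.1 names assignment of the study ID before randomization, and section 5.4.1 calls these items baseline assessments. Section 5.4.1.2 also uses the same kind of phrase, within a stated interval of randomization, for laboratory tests that Appendix C puts before enrolment. This stands as evidence of intent. It does not settle the order, because no sentence does.

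Several stronger readings are tempting and are not supported:

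- **That the planned FACIT comparison is biased.** It is not, because the baseline does not enter it. Bias from this source arises only if a baseline-dependent analysis is used.
- **That the size of such a bias can be stated.** The 5.51-point figure in section 2.1.7 is a difference between hemoglobin groups, not an expected effect or a margin, and no passage supports any particular shift.
- **That Appendix C puts randomization first because its row is higher.** Rows are grouped by type. Randomization also sits above laboratory tests done before enrolment.
- **That the bleeding subgroup is contaminated.** Section 5.4.1.1 records bleeding over the past 2 months, whereas section 8.2 defines the subgroup by ongoing bleeding. Nothing links the two. Medical history is in any case a lesser matter: history relevant to exclusion is asked at screening, and many other items are factual.
- **That chance imbalance in baseline fatigue is a bias.** It is sampling error, already covered by the confidence interval. The cost is width.

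It is also fair to say that the plan is silent on using the baseline rather than opposed to it, and that follow-up FACIT is reported with the arm known whatever the order. The 7-day recall softens the effect of completion soon after disclosure but does not remove it.

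**Conclusion.** The point holds as a free improvement to a secondary outcome. The schedule leaves open whether baseline FACIT comes before or after the arm is known, and the outcome as written does not use that baseline. The present comparison is not biased as a result. It is less precise than it could be, and a baseline-adjusted analysis chosen later would depend on a score not protected from knowledge of allocation.

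With 18 per arm, adjustment cuts the half-width by about 5%, 13% or 29% for ρ of 0.3, 0.5 or 0.7 (from 1 − √(1 − ρ²)). This rests on the SDs in section 2.1.7 applying here, equal SDs at baseline and follow-up, a normal approximation, and assumed correlations, since the documents report none. The primary outcome, time to enrol 52 patients, and the sample size are unaffected.

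**What to change.** Make both changes together, because using the baseline without protecting it would open the route to bias that the present definition avoids.

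- **Section 5.4.1.1 and Appendix C:** require FACIT-fatigue to be completed and dated after consent and before the randomization envelope is opened, whether the visit is in person or remote. Show this in the schedule as a pre-randomization step. Do the same for medical history, as a lesser point.
- **Section 7.2 item 13 and section 8.2:** compare FACIT between arms at weeks 4, 8 and 12 adjusted for the pre-randomization score (ANCOVA), rather than as raw scores or simple changes.

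The cost is a reordering of steps already planned, an edit to the schedule and a sentence or two in the outcome and analysis sections. No assessment or patient is added.
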